Safety assessments	
 • Evaluation of all AEs and SAEs including infusion site and hypersensitivity reactions • Physical examination • Vital signs, height and weight • Laboratory evaluations • Electrocardiogram (ECG) • Echocardiogram (on patient enrolled prior to Amendment #3) • X-ray assessment of surgical complications (if applicable) and complications of fracture healing
Other assessments	[REDACTED]
Data analysis	
The primary variable is change from baseline in Total LBM at Week 24.
 
A mixed model will be used with change from baseline at all post-baseline visits (Week 12 and Week 24) as response variable, and treatment, visit, randomization strata and baseline measurements as covariates. Two interaction terms (treatment*visit and baseline LBM*visit) will also be included in the model. The two-sided p-value for the least square mean (LSM) difference between the bimagrumab and the placebo groups at

Protocol number	CBYM338D2201
	
Week 24 (and at Week 12) will be reported for the difference. Holm-Bonferroni method will be used to adjust for type I error among the 2 comparisons (bimagrumab 210 mg vs. placebo and bimagrumab 700 mg vs. placebo). Total LBM data will be transformed with natural logarithm before this analysis. The bimagrumab 70mg group will not be used for hypothesis testing.
 
[REDACTED]
 
The change in gait speed from baseline will be analyzed similar to the primary variable. If the variable is not normally distributed, log transformation may be used if warranted.
 
The change in summary performance score of SPPB and in each one of the component scores (balance test score, gait speed score, chair stand score) from baseline will be analyzed similar to the primary variable, assuming a normal distribution. If the variable is not normally distributed, log transformation may be investigated.

Key words	Bimagrumab, BYM338, hip fracture, elderly, controlled clinical trial, randomized, muscle wasting (atrophy)

1 Introduction

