9.5 Analysis of secondary [REDACTED] variables

9.5.1 Efficacy variables

9.5.1.1 Gait speed and Short Physical Performance Battery (SPPB)

The change from baseline at Week 24 and Week 48 in gait speed and in SPPB will be analyzed similar to the primary variable. A log transformation may be used if warranted. An unstructured within subject correlation structure will be used for the covariance matrix.

In addition, dose response modeling will be performed for both gait speed and SPPB using the MCP-Mod approach.

The following testing strategy will be used to control for multiplicity of endpoints and doses to be tested: if both doses (210 and 700 mg) are statistically significantly different from placebo at $\alpha=0.05$ two-sided for the primary endpoint, then a fixed sequence approach will be applied for both Gait Speed and Short Physical Performance Battery (SPPB) at week 24 using the same linear mixed model for repeated measures and $\alpha=0.05$ two-sided at each stage. The first inference will compare the 700 mg group to placebo for Gait Speed, followed by a second inference comparing the 210 mg group to placebo for Gait Speed. The third inference will compare the 700 mg group to placebo for SPPB, followed by a fourth inference comparing the 210 mg group to placebo for SPPB. Additionally, the fifth inference will compare the combined 700 mg and 210 mg group to placebo for the incidence of fall observed till the time of the interim analysis. The analysis conducted at Week 24 for falls will include available incidence of falls also collected from patients with visits beyond Week 24. The analysis of the fall data will be performed based on the assumption that the differences in incidences of fall within the active bimagrumab doses (700 mg and 210 mg) is small compare to the differences of those doses to the placebo arm.

The sequence of the endpoints has been decided based on the anticipated probability of showing statistical significance of bimagrumab over placebo, the clinical importance is not considered for this sequence determination, as each endpoint is clinically important.

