2.4 Formal planned analyses

2.4.1 Primary analysis

The primary analysis will be performed when all patients have completed the double-blind treatment epoch (Week 24 [EOT] assessments regardless of treatment completion or premature discontinuation of treatment/study in the 24-week treatment epoch). The [REDACTED] biostatistics team will be unblinded at patient level to conduct the primary analysis (whereas selected members of the Novartis global team will only be unblinded at group level). Patients, site personnel and country investigators will remain blinded until the final database lock. An independent global clinical person will have access to individual randomization codes after the primary analysis.

Assignment and authorization (per [REDACTED] internal procedure) of patients to the different analysis sets, [REDACTED], will be performed prior to the unblinding of the treatment code and start of the primary analysis. At the time of the primary analysis, subgroups with a stratification level containing less than five patients will be suppressed and only the count (n) will be displayed. In addition, minimum and maximums in tables will be suppressed. These measures are to avoid potential unblinding of the selected members of the Novartis global team. Details of the level of unblinding, including identification of unblinded contact personnel in both teams will be included in a separate unblinding plan created by the [REDACTED] biostatistics team.

All data will be included in the data transfer for the primary analysis. By-visit data up to and including Week 24 will be cleaned at that time whilst other data such as AEs and concomitant medications (CM) will be as clean as is feasible, following data checks. In addition, at the time of the primary analysis, some patients may still be ongoing or may even have completed the post-treatment follow-up epoch. As such, by-visit data following Week 24 will also be included in the data transfer, as relevant although limited queries may still be outstanding and it is accepted that the data are not in clean, locked state. All AE and CM data available at the time of the primary analysis will be included in the data transfer. The [REDACTED] biostatistics team will ensure that the state of all data received in the data transfer at the time of the primary analysis is as expected.

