2.10.2.3 Statistical model, hypothesis, and method of analysis (secondary)

The change from Baseline in derived gait speed (m/sec) and change from Baseline in total SPPB score at each windowed post-baseline visit will be analyzed using an MMRM in a similar manner to the primary efficacy variable (as specified in [Section 2.10.1.3](#) [Statistical model, hypothesis, and method of covariate analysis]). Treatment group, visit, region (Japan/Non-Japan), treatment date (early/late), fracture fixation type (internal [screws only, intramedullary {nails} and extramedullary fixation {plate, combinations}]/arthroplasty [hemiarthroplasty or total hip arthroplasty]), history of falls (yes/no [none]), use of mobility aids prior to hip fracture (yes/no [none]) and Baseline value will be included as covariates (see “Covariates” column of Table 2.2 [[Section 2.6](#) {Subgroups}]). In addition, the following six interaction terms will be fitted:

- Treatment group*visit.
- Region*visit.
- Treatment date*visit.
- Fracture fixation type*visit.
- History of falls*visit.
- Use of mobility aids prior to hip fracture*visit.
- Baseline value*visit.

An unstructured covariance matrix will be used for the Week 12 analyses, Week 24 analyses (primary analysis) and Week 48 analyses (final update analysis). The underlying assumptions of the mixed model (homogeneity of slopes and normality) will be assessed by the normality of the residuals within treatment groups. The homogeneity of the variance will be checked by Levene's test at the time of the primary analysis. If the variable is not normally distributed,

natural log transformation may be used (see [Section 3.11.1](#) [Mixed Model Repeated Measures {MMRM}]) for more details on how to assess normality). The antilog of the point estimate and associated 95% confidence interval of the treatment difference will be computed prior to presentation.

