Other variables (derived gait speed [m/sec], total SPPB, [redacted] [g/cm²], [hip]) will be analyzed with a similar MMRM model as used for change from Baseline in total LBM (kg), including appropriate windowed post-baseline visits (repeated measures) and additional covariates, as specified in [Section 2.10.2.3](#) (Statistical model, hypothesis, and method of analysis [secondary]). If the primary efficacy endpoint is significant, the testing strategy, as described in [Section 2.10.2.3](#) (Statistical model, hypothesis, and method of analysis [secondary]), will be used to control for the fact that we have two secondary endpoints:

If both doses (bimagrumab 700 mg and bimagrumab 210 mg) are statistically significantly different from placebo at $\alpha = 0.05$ two-sided for the primary endpoint, then a step down approach will be applied for both derived gait speed (m/sec) and total SPPB score at Week 24 using the same linear MMRM.

For derived gait speed (m/sec), the L matrix coefficients for the LSMEANS are as follows: Baseline derived gait speed: 0.4682 m/sec; Visit (either 12, 24, 36 or 48 weeks): 1; Geographic Region (either Japan or Non-Japan): Non-Japan; Treatment date (either Early or Late): Late; Fracture fixation type (Arthroplasty or Internal): Internal; History of falls (12 months): (either Yes or No): No; Use of mobility aids prior to hip fracture (3 months) (Yes or No): No.

For total SPPB score, the L matrix coefficients for the LSMEANS are as follows: Baseline total SPPB score: 5.5804; Visit (either 12, 24, 36 or 48 weeks): 1; Geographic Region (either Japan or Non-Japan): Non-Japan; Treatment date (either Early or Late): Late; Fracture fixation type (Arthroplasty or Internal): Internal; History of falls (12 months): (either Yes or No): No; Use of mobility aids prior to hip fracture (3 months) (Yes or No): No.

Total LBM (kg) data will be transformed with natural logarithm before analysis. The residuals from the MMRM analyses, are to be visually checked for normality and homogeneity of variance. For derived gait speed (m/sec) and total SPPB score, normality is to be examined by normal probability plots, while homogeneity of variance is to be assessed by plotting the residuals against the predicted values for the model and via Levene's test using the following example SAS[®] code:

```
proc glm data = ....;
class trt;
model y = trt;
means trt / hovtest=levене;
run;
```

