If the data is not normally distributed, this data will also be transformed with natural logarithm before analysis. The antilog of the point estimate and associated 95% confidence interval of the active treatment versus placebo treatment difference will be computed prior to presentation.

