Appendix 1: Efficacy assessments: Performance and assessment details

SPPB

The short physical performance battery (SPPB) contains five physical functional exercises for the lower extremities divided into three functional components: Total standing balance, gait speed and chair stand. A score will be derived (derived by the [REDACTED] biostatistics team) for each of the three components. In addition, a total SPPB score will also be calculated (derived by the [REDACTED] biostatistics team). The total SPPB score is calculated as the sum of its component scores:

- Total standing balance score.
- Gait speed score.
- Chair stand score.

The total SPPB score will only be calculated if a score is available for each of the three functional component scores.

Standing balance

In each case the lowest possible value is zero (0). Higher values correspond to better functional condition. Total standing balance score is calculated as the sum of the scores of side-by-side stand, semi-tandem stand and tandem stand.

- Side-by-side stand: Held for 10 sec = 1 point, not held for 10 sec or not attempted = 0 points.
- Semi-tandem stand: Held for 10 sec = 1 point, not held for 10 sec or not attempted = 0 points.
- Tandem stand: Held for 10 sec = 2 points, held for 3 to 9.99 sec = 1 point, held for less than 3 sec or not attempted = 0 points.

Handling of missing data: If a test is not done (i.e. test not done is ticked in the eCRF) there will be no imputation of data. If “Side by side stand” is reported as “Not held for 10 seconds”, or “Not attempted”, then the results for “Semi-tandem stand” and “Tandem stand” should be missing. Since the standing balance tests become progressively more difficult with each test, starting from the easiest (“Side-by-side stand”), if the result for the tandem stand or semi-tandem stand is missing the result will be imputed by 0 points, provided that the previous test(s) had been performed. In all other cases there will be no imputation.

Gait speed

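### The scale of the confirmatory gait-speed and SPPB tests is not fixed in advance, and the log fallback is undefined when total SPPB is 0

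*SAP*

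**What the plan says.** SAP 2.10.2.3 and protocol 9.5.1.1 set a fixed sequence at two-sided 0.05, entered only if both doses succeed on lean body mass. Gait speed (700 mg, then 210 mg) and SPPB (700 mg, then 210 mg) are its first four tests; falls are the fifth.

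On the scale of those four tests the documents say:

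- SAP 3.11.1: "If the data is not normally distributed, this data will also be transformed with natural logarithm before analysis".
- SAP 2.10.2.3, if the variable is not normal: "natural log transformation may be used".
- Protocol 9.5.1.1: "A log transformation may be used if warranted".
- Protocol synopsis, data analysis, for SPPB: "If the variable is not normally distributed, log transformation may be investigated".

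On the criterion, SAP 2.10.2.3 says the assumptions "will be assessed by the normality of the residuals within treatment groups", and SAP 3.11.1 that "normality is to be examined by normal probability plots". Levene's test is planned for the time of the primary analysis, with treatment as the class variable in the example code, but neither section ties its result to the transformation. There is no cut-off, and no rule for the case where only one arm, visit or endpoint fails. SAP 2.4.1 adds that the "biostatistics team will be unblinded at patient level to conduct the primary analysis".

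SAP Appendix 1 lets each of the three SPPB components score 0, and the lowest category of the total starts at 0. No offset or other treatment of zero is given. A failed timed test leaves the time missing.

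**The concern.** A confirmatory test should have one scale, named before anyone can see results by arm. SAP 2.10.1.3 does this for lean body mass: logs are taken first, then the change, with baseline logged too. For gait speed and SPPB the scale depends on a judgement about plots, under wording that is mandatory in one place and discretionary in three.

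Three things are at stake. The sequence stops at its first failure, so the scale used for gait speed at 700 mg can decide whether anything after it is tested. An SPPB of 0 is an observed result meaning no measurable function, and a log analysis cannot use it. A log analysis also changes the question: the objectives, the meaningful differences and the power statements are in m/s and points, and the back-transformed result is a ratio.

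**Working it through.** **1. The plan's own power figures.** SAP 2.13 and protocol 9.7 give 0.15 m/s with SD 0.25 and 1.0 point with SD 1.5, 70 per arm, two-sided 0.05. Power is Φ(d / (SD·√(2/n)) − 1.96).

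- Gait speed: 0.15 / (0.25 × 0.1690) = 3.55; Φ(1.59) = 94.4% (94.1% by noncentral t). Stated: 94%.
- SPPB: 1.0 / (1.5 × 0.1690) = 3.94; Φ(1.98) = 97.6% (97.5% by noncentral t). Stated: 97%.

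Both reproduce, and both describe a difference on the original scale. At 60 per arm (15% dropout) the same formula gives 90.8% and 95.5%.

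**2. Timing.** The trigger is non-normality of residuals within treatment groups. Residuals from a model containing treatment, viewed by arm, require treatment codes. The team running that model is unblinded at patient level for the primary analysis, and no blinded decision step is described.

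**3. Zeros.** Following the lean-body-mass convention, the outcome would be log(follow-up) − log(baseline). A follow-up total of 0 makes that visit's record undefined; a baseline of 0 makes all of the patient's records undefined. If the log were applied to the change itself, zero and negative changes would be undefined as well.

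**4. Meaning.** log(3/1) = log(12/4), so a gain of 2 points and a gain of 8 points count equally on the log scale.

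**5. Simulation.** 10,000 two-arm trials per setting, 60 per arm, ANCOVA of change on arm and baseline, one follow-up visit.

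- From the documents: change SDs 0.25 m/s and 1.5 points; baseline means 0.47 m/s and 5.58 points (SAP 3.11.1); baseline SPPB SD 2.8 (SAP Table 2.5).
- Assumed: lognormal baseline gait speed with SD 0.25; placebo gains of 0.25 m/s and 1 point; normal changes; SPPB rounded, held to 1–12 at baseline and 0–12 at follow-up. Zeros (1.0–1.6% of follow-up scores) were dropped on the log scale.
- The switch used Shapiro-Wilk at 0.05 on residuals pooled over arms.

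| % of trials significant | Gait, no effect | Gait, 0.15 m/s | SPPB, no effect | SPPB, 1.0 point |
|---|---|---|---|---|
| Original scale | 5.0 | 90.1 | 4.8 | 93.2 |
| Log scale | 4.9 | 82.7 | 4.9 | 84.5 |
| Switch by normality test | 5.1 | 89.9 | 4.8 | 91.4 |
| Either scale | 7.0 | 91.3 | 7.2 | 94.3 |

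The Monte Carlo standard error at 5% is √(0.05 × 0.95 / 10,000) = 0.2 points. Under the planned effects the two scales disagreed on significance in 9.7% (gait speed) and 11.0% (SPPB) of trials.

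**6. Sensitivity to the zero rule.** 4,000 SPPB trials per setting, 1.0-point effect, with an assumed share of follow-up scores set to 0 at random in both arms. Power in %:

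| Zeros | Original | Log, zeros dropped | log(x+1) | log(x+0.5) |
|---|---|---|---|---|
| 0% | 93 | 86 | 89 | 88 |
| 2% | 78 | 85 | 55 | 48 |
| 5% | 60 | 84 | 31 | 24 |
| 10% | 42 | 82 | 20 | 16 |

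The unstated zero rule can matter more than the choice of scale.

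**The case against.** The log is only a fallback. SAP 3.11.1 evaluates the least-squares means at untransformed baselines (0.4682 m/s and 5.5804 points), the antilog presentation is pre-specified, and descriptive changes in original units are reported anyway. Residuals have the group means removed, so a normality plot does not directly display the treatment effect. These are secondary endpoints in a phase II trial, gated on both doses. All of this stands and limits the harm, but it does not settle which scale decides the test.

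Three stronger readings are tempting and are not supported.

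- **That the rule inflates type I error to 7%.** The stated trigger is residual shape, not significance, and a switch driven by a normality test stayed at 5.1% and 4.8%. About 7% requires picking the more favourable scale. The discretionary wording does not exclude that, but nothing prescribes it.
- **That the SAP says the choice is made after unblinding.** It does not date the decision; the phrase about the time of the primary analysis belongs to Levene's test. The timing is a firm inference from what the check needs.
- **That patients who lose all function leave the analysis, for both endpoints.** Derived gait speed loses no one extra, because a failed walk is missing on either scale. For SPPB, a later zero removes that visit's record, not the patient. Baseline zeros should be few, since entry requires completing a 4 m walk at screening.

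**Conclusion.** The point holds as an unfixed scale for four confirmatory tests, with a fallback that cannot be computed for some observed SPPB scores. The conflict between *will* and *may* and the missing criterion and zero rule can be read directly from the text.

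If the log is used, the cost in these simulations is about 7 points of power for gait speed (90% to 83%) and 9 for SPPB (93% to 84%), and the answer becomes a ratio that the stated powers do not cover. A purely mechanical switch would cost little in either error rate or power.

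The sizes rest on ANCOVA at one visit in place of the repeated-measures model, and on the assumed baseline shape and placebo gains. The share of SPPB zeros is unknown. They were placed at random, so the results show dependence on the zero rule and do not measure bias; bias would arise if zeros differed by arm.

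**What to change.** Before unblinding, state in SAP 2.10.2.3 and 3.11.1 that the untransformed change from baseline is the confirmatory analysis for gait speed and total SPPB, and delete the log switch. Align the protocol synopsis and 9.5.1.1, which otherwise keep the same discretion. Report any log analysis (gait speed only), rank-based analysis or bootstrap as a sensitivity analysis, whatever the residual plots show.

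This costs wording only and keeps the basis of the stated powers. The downside is somewhat less efficient inference if residuals are strongly skewed. A numeric criterion applied at a blinded review, with a stated rule for SPPB zeros, would also close the gap in specification, but it would leave open whether the result is a difference or a ratio.

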3.11.2 Pattern mixture model

A pattern-mixture model based on non-ignorable missing, i.e. “missing not at random” (MNAR) will be used, where all premature discontinuations due to AE, death (D) or unsatisfactory therapeutic effect (UTE) of the active treatment groups are assumed to behave like placebo treatment group patients after study discontinuation. Premature discontinuation of all other patients (not related to AE, D or UTE) will be imputed under MAR. Both approaches will be implemented by multiple imputations, where missing values are multiply replaced by sampling from the Bayesian posterior predictive distribution based on the model. Each of the completed datasets is then analyzed using the primary analysis model, and then the estimates are combined using Rubin's rules to get the final inference.

In general, 4 programming steps will be performed using the SAS procedures MI, MIXED, and MIANALYZE:

Step 1: Impute missing data to obtain a monotone missing data pattern for all patients.

```
proc mi data = ... out=_imp1 nimpute=100 seed=...;
by trtn;
mcmc chain = multiple impute=monotone;
var BSL VIS12 VIS24;
run;
```

where BSL implies Baseline value, VIS12 implies value at Week 12 and VIS24 implies value at Week 24.

The resulting output dataset _imp1 will have 100 copies of the original dataset of patients where each copy will have a monotone missing pattern.

Step 2:

(2.1) Standard multiple imputation based on the treatment-specific information will be used for patients in active treatment groups who prematurely discontinued the study for other reasons than AE, D or UTE and for patients in the placebo treatment group.

```
data _imp2a;
set _imp1 (where=(trtn eq 0))
_imp1 (where=(trtn ne 0 and aedute ne 1));
run;

proc sort data=_imp2a;
by _imputation_;
run;

proc mi data=_imp2a out=IMPOTH nimpute=1 seed=...;
by _imputation trtn;
class trtn;
monotone regression;
var BSL VIS1 VIS12 VIS24;
run;
```

(2.2) It is suggested that patients on active treatment who prematurely discontinue due AE, D or UTE behave like patients on placebo after study discontinuation (leading to a placebo-based pattern imputation). Imputation model for these data will be built only on data from the placebo treatment group. It imputes missing data in active treatment groups using a single control-based imputation model.

```
data _imp2b;
set _imp1 (where=(trtn eq 0))
_imp1 (where=(trtn ne 0 and aedute eq 1));
run;

proc sort data=_imp2b;
by _imputation_;
run;

proc mi data=_imp2b out=IMPPRDISC nimpute=1 seed=...;
by _imputation trtn;
class trtn;
var BSL VIS1 VIS12 VIS24;
monotone regression;

mnr model (VIS1 / MODELOBS =(trtn=0));
mnr model (VIS12 / MODELOBS =(trtn=0));
mnr model (VIS24 / MODELOBS =(trtn=0));

run;
```

(2.3) Pool the above datasets.

```
data allimp;
set IMPPRDISC
IMPOTH;
by _imputation_;
run;
```

Step 3. Analyze Week 24 data by using the complete dataset derived from Step 2.

```
proc mixed data=allimp order=internal;
by _imputation_;
```

```
class sidla trtn vis_1n region trtdt ████ frclass frfix histfall mobaid;
model chg_1n = trtn vis_1n bsval regi ████ trtdt trtn*vis_1n bsval*vis_1n
region*vis_1n trtdt*vis_1n / ddfm=kr solutionf covb ;
repeated vis_1n / patient=sidla type=un;
lsestimate trtn*vis_1n
'BYM388 700 mg - Pbo, Baseline' -1.....0 1.....0 0.....0 0....0 ,
'BYM388 210 mg - Pbo, Baseline' -1.....0 1.....0 0.....0 0....0 ,
'BYM388 70 mg - Pbo, Baseline' -1.....0 0.....0 1.....0 0....0 ,
'BYM388 700 mg - Pbo, Week12' -1.....0 1.....0 0.....0 0....0 ,
'BYM388 210 mg - Pbo, Week12' -1.....0 1.....0 0.....0 0....0 ,
'BYM388 70 mg - Pbo, Week12' -1.....0 0.....0 1.....0 0....0 ,
'BYM388 700 mg - Pbo, Week24' -1.....0 1.....0 0.....0 0....0 ,
'BYM388 210 mg - Pbo, Week24' -1.....0 1.....0 0.....0 0....0 ,
'BYM388 70 mg - Pbo, Week24' -1.....0 0.....0 1.....0 0....0 ,
;/ cov
run;
```

Step 4. Combine the results from Step 3 analysis on 100 imputed datasets to derive an overall result.

```
data cov_MI;
set lsestimate (keep = coll - coll15);
run;
```

```
data estimate_MI;
set lsestimate (keep = estimate);
run;
```

```
proc mianalyze parms=estimate_MI;
class trtn;
modeleffects trtn;
format trtn trt_.;
by vis_1n;
run;
```

```
proc mianalyze parms=cov_MI;
class trtn;
modeleffects trtn bsval region;
format trtn trt_.;
by vis_1n;
run;
```

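### The SAP's printed program for the MNAR sensitivity analysis of total LBM counts every placebo patient twice and gives the placebo-based imputation no placebo records in the active arms

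*SAP*

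**What the plan says.** Protocol 9.4.3, SAP 2.10.1.5 and the text of SAP 3.11.2 agree on the method. Active-arm patients who discontinue for adverse event, death or unsatisfactory therapeutic effect are assumed to behave like placebo patients afterwards. All other missing values are imputed under MAR by treatment. Each completed dataset is analysed with the primary model and the results are combined by Rubin's rules.

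The steps printed in SAP 3.11.2 are:

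- Step 1 makes the missing pattern monotone, with 100 imputations and the variables "var BSL VIS12 VIS24".
- Step 2.1 is, by its text, for active patients who discontinued "for other reasons than AE, D or UTE and for patients in the placebo treatment group". Its input `_imp2a` starts with "set _imp1 (where=(trtn eq 0".
- Step 2.2 is the placebo-based step: "Imputation model for these data will be built only on data from the placebo treatment group". Its input `_imp2b` starts with the same placebo line. The PROC MI call runs "by _imputation trtn" and limits the model observations with "mnr model (VIS24 / MODELOBS =(trtn=0" and matching lines for the other visits.
- Step 2.3 pools the outputs with "set IMPPRDISC" followed by `IMPOTH`, by imputation, with no condition on treatment.
- Step 3 passes the pooled `allimp` to PROC MIXED with "repeated vis_1n / patient=sidla type=un".

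**The concern.** Three things in the code conflict with the text.

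1. **Placebo is pooled twice.** Placebo rows are needed in `_imp2b` so that a placebo model can be fitted, but they should be dropped again before pooling, because step 2.1 already supplies them. Nothing printed drops them.
2. **The placebo model is out of reach.** BY processing splits the data by treatment before the model is fitted. An active-arm group cannot contain a record with `trtn=0`, so the donor restriction selects nothing in exactly the groups it was written for.
3. **VIS1 has no source.** Both step 2 PROC MI calls list VIS1, which step 1 does not carry. LBM is measured only at Day 1, Week 12 and Week 24, and SAP 3.11.1 codes visit 1 as baseline. VIS1 is therefore either undefined or a second copy of BSL. This is minor.

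The primary LBM analysis assumes MAR. Protocol section 4 expects about 200 of 245 patients to complete Week 24, so about 45 may have no Week 24 value. The planned completers analysis does not test departures from MAR; this analysis is the only one that does. SAP 2.10.2.4 also says the gait speed and SPPB sensitivity analyses follow the LBM approach, so the same code may be reused there.

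**Working it through.** The plan states no figure for this analysis, so there is none to reproduce. The two main faults are read from the code; no SAS was run. Odd spellings (`mnr`, `_imputation` without its final underscore, `patient=` where SAS expects `subject=`) may come from editing or text extraction and carry no weight here.

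**Inputs.** Planned arm sizes from SAP 2.13: placebo 70, 70 mg 35, 210 mg 70, 700 mg 70, total 245.

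**Step A: patient copies per imputation.**

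- `_imp2a` holds all placebo patients plus active patients with `aedute` not 1.
- `_imp2b` holds all placebo patients plus active patients with `aedute` equal to 1.
- The two active subsets do not overlap and together give 35 + 70 + 70 = 175 patients, each once. Placebo contributes 70 + 70 = 140.
- Pooled: 175 + 140 = 315, where 245 is correct. The placebo share is 140/315 = 44.4% instead of 70/245 = 28.6%.

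These counts do not depend on how many patients have `aedute` equal to 1.

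**Step B: donors in step 2.2.** Within one imputation, the placebo BY group has 70 records with `trtn=0`. Each of the three active BY groups has 0. With treatment removed from the BY statement, the single group has 70 donors.

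**Step C: effect of the duplicates in PROC MIXED.** The reshape to one row per visit is not printed. With blocks formed by `sidla`, a duplicated patient has two Week 12 and two Week 24 records. If S is the 2×2 unstructured covariance of the two visits, the patient's 4×4 block is

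[ S S ; S S ].

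Its last two rows repeat the first two, so its rank is 2 and its determinant 0 for any positive-definite S. A numerical check with unit variances and correlation 0.6 gives the same. The likelihood needs the inverse of this block, so the fit should fail or degenerate.

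**Step D: only if the copies were given separate identifiers.** The standard error of an active-versus-placebo difference, relative to the correct one, with complete data and equal variances, is

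sqrt(1/70 + 1/140) / sqrt(2/70) = sqrt(0.75) = 0.866, which is 13% too small.

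- Coverage of a nominal 95% interval: 2Φ(1.96 × 0.866) − 1 = 0.910.
- A nominal two-sided 0.05 becomes about 0.090, and 0.025 becomes about 0.052.

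A simulation adds missing data: 4,000 null trials, 45/245 = 18.4% missing at Week 24, 10 imputations, ANCOVA at Week 24 and Rubin's rules. It assumes that half of the active-arm missing values are due to adverse event, death or unsatisfactory effect, and that the placebo-based step works as intended. The mean SE is 0.159 with duplicates against 0.184 without (ratio 0.863). Coverage is 93.1% against 96.6%. The SE ratio is stable at about 0.86, but coverage with duplicates moves between about 91% and 95% as the assumed dropout changes, so 93.1% is only illustrative.

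**The case against.** The strongest reply is that this is an outline and not a program. It is introduced as a general sequence of steps, has placeholder dataset names and seeds, identical contrast strings for the 700 mg and 210 mg rows, and no reshape. No result can come from it without rewriting, and the prose fixes the method correctly in three places. On this view, aligning the code with the text is ordinary debugging. The SAP version log also records two dry runs of outputs before the final version, so faults may have been found before unblinding. Finally, the SE and coverage figures describe a repair that nobody has proposed.

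Part of this stands. The consequences are inferred, and a repair after unblinding is a risk, not an established fact: SAP 2.4.1 unblinds the biostatistics team at patient level to run the primary analysis, but the log does not say whether this output was in the dry runs. The figures in Step D are conditional, and the simulation uses fewer imputations and a simpler model than the SAP. A singular block would show itself, whereas a narrow interval would not.

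The outline argument does not dispose of the two faults. These lines are present and wrong; they are not gaps left for the programmer. Nothing printed corrects them, they remain in the SAP after both dry runs, and the separate programming specifications (RAP Module 8) are cited only for date imputation.

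**Conclusion.** The concern holds. The printed code for the LBM pattern-mixture analysis does not carry out the method in its own text. Each imputation contains 315 patient copies instead of 245 because all 70 placebo patients enter twice, and the placebo-based imputation has no donors in any active arm. Both follow from the printed lines and the planned arm sizes alone.

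As printed, the likely result is a run that fails or degenerates. The 13% understatement of the standard error applies only if someone gives the copies separate identifiers, and it assumes 70 analysed per group.

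The damage is confined to this sensitivity analysis and any reuse of its code. The primary MMRM, the Holm-Bonferroni adjustment and the stated power are untouched. It should be fixed, because it is the only check of the MAR assumption behind the primary result.

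**What to change.** Change SAP 3.11.2 as follows:

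- **Step 2.3:** `set IMPOTH IMPPRDISC(where=(trtn ne 0)); by _imputation_;` so that placebo rows come from step 2.1 only. Filter on treatment and do not rely on removing identical rows, because a placebo patient with missing values may receive different draws in the two PROC MI calls.
- **Step 2.2:** run PROC MI `by _imputation_` alone and keep `trtn` in CLASS, so that MODELOBS can reach the placebo records. The BY treatment in step 2.1 is right and stays, since that step is treatment-specific MAR.
- **VIS1:** remove it from both step 2 PROC MI calls, together with its MNAR model line.
- **Check before PROC MIXED:** confirm that each imputation holds each FAS patient exactly once per visit (245 patients if enrolment is as planned).

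The cost is a few lines of SAP code and one count. No new data or patients are needed, and the method described in the text does not change.
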